7.2.2. Primary Analysis of the Primary Endpoint

The primary efficacy analysis for this study is designed to test the scientific hypothesis that rituximab has a beneficial clinical impact on SSc-PAH as measured by improvement or stabilization in 6MWD between baseline to 24 weeks in patients treated with standard of care plus rituximab than in patients treated with standard of care plus placebo. Operationally for this study, this scientific hypothesis will be examined by formally testing the following statistical hypothesis:

H_0 : The mean change in 6MWD between baseline and 24 weeks does not differ between individuals treated with rituximab and those treated with placebo
($\bar{\delta}_{\text{rituximab}} = \bar{\delta}_{\text{placebo}}$ where $\bar{\delta}_x = \text{mean 6MWD at 24 weeks} - \text{mean 6MWD at baseline}$)

versus

H_A : The mean change in 6MWD between baseline and 24 weeks is more beneficial in those individuals treated with rituximab than in those treated with placebo
($\bar{\delta}_{\text{rituximab}} < \bar{\delta}_{\text{placebo}}$ where $\bar{\delta}_x = \text{mean 6MWD at 24 weeks} - \text{mean 6MWD at baseline}$)

While this hypothesis is inherently one-sided, a two-sided test at $\alpha=0.05$ will be used to evaluate the treatment effect at 24 weeks. This primary hypothesis will be tested using a repeated measures random effect model to model the distance walked as a function of treatment, visit week and a treatment by visit week interaction. Additionally, a quadratic term for visit week will be included in the model. A random slope and intercept will be fit for each subject using a separate unstructured covariance matrix for each treatment group. The model will include only 6MWD data up to Week 24. All available data up to Week 24 will be used for subjects who terminate early from the study. All unscheduled visits that occur prior to Week 24 will also be included in the analysis.

Model estimates and standard errors of the distance walked and change from baseline in distance walked will be presented at baseline and Week 24, along with the differences between arms. An appropriate contrast will be used to test the difference (baseline to Week 24) between treatment arms.

Distance walked and change from baseline in distance walked will be shown graphically by treatment arm. Spaghetti plots and summary statistics including 25th percentile, mean, median, and 75th percentile will be plotted for each visit by treatment group. Additionally, mean predicted values from the model will be plotted over time, alongside the actual distance walked values for each study visit.

The primary efficacy analysis will be based on the ITT population.

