Sample Size: The study will include 30 subjects treated with rituximab and 30 subjects treated with placebo.

Data Analyses: The primary efficacy analysis of change in 6MWD from baseline to 24 weeks will be performed on the intention-to-treat (ITT) population, and will be tested using a repeated measures random effects model to model change from baseline in 6MWD as the primary outcome and treatment as the primary predictor, controlling for visit day, limitations by musculoskeletal disease, baseline levels of 6MWD, and a treatment by visit day interaction. A random slope and intercept will be fit for each subject. An unstructured covariance matrix will be assumed for the random effects. Additional covariates will be considered for this model as part of secondary analysis.

[figure not shown]
Secondary analyses will include repeating the primary analysis in the per protocol population, subgroup analyses of the primary outcome, safety analyses, exploratory analyses of the secondary endpoints, and exploratory analyses of the mechanistic endpoints.

Lay Summary:

Sixty eligible adults between the ages of 18 and 75 who have been diagnosed with SSc-PAH within the past 5 years and meet all entry criteria will be enrolled in this study. Participants will receive 2 infusions (1000 mg) of either rituximab or placebo 14 days apart.

This study will compare patients treated with rituximab to those on placebo for change in six minute walk distance (6MWD). The secondary objectives of this study are to compare treatment groups for other measures of clinical disease progression and to determine whether the effects on clinical disease progression are paralleled by changes in selected biomarkers. Additionally, the safety and tolerability of rituximab for the treatment of SSc-PAH in patients receiving stable background medical treatment with prostanoid, endothelin receptor antagonist, PDE-5 inhibitor, and/or guanylate cyclase stimulators therapy will be assessed.

FLOW DIAGRAM OF PROTOCOL

ABBREVIATIONS

6MWD	6-Minute Walk Distance
6MWT	6-Minute Walk Test
ACE	Autoimmunity Centers of Excellence
ADCC	Antibody-dependent Cellular Cytotoxicity
ADCT	Autoimmune Diseases Clinical Trials
AE	Adverse event
AECA	Anti-Endothelial Cell Antibody
ALP	Alkaline Phosphatase
ALT	Alanine Aminotransferase
ANAs	Serum Antinuclear Antibodies
ANCOVA	Analysis of Covariance
Anti-B23	Antibody to the B23 antigen
Anti-CENP-B	Antibody to the CENP-B (centromere) antigen

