3.1.1 Stratification, Randomization, and Masking

Subjects will be randomized in a 1:1 ratio to receive 2 infusions 14 days apart of either rituximab 1000 mg (treatment arm) or placebo (control arm). The automated randomization system will implement an adaptive randomization procedure to maintain balance between treatment groups overall, by study site, with respect to disease severity as measured by PVR at baseline, and with respect to time since diagnosis of SSc-PAH.

To maintain study blind, the appearance of the packaging and solutions used to administer study drug/placebo will be identical in both study arms.

All clinical and immunology laboratory staff will be masked to the treatment assignments until the completion of the study. In addition, immunology laboratory staff will not have access to any clinical results and clinical staff members, including the investigators, will not have access to any immunology lab results until completion of the study. B cell recovery status and the need for quarterly monitoring visits as defined in Section 6.5.4.12, *Visit 16 [Week 48]* will be communicated to clinical staff upon completion of Visit 16 or Early Endpoint visit. If B cells have not recovered by two years after treatment initiation, B cell levels will be provided to the clinical staff.

Individual treatment assignments will not be unmasked until all subjects have completed the study. In the event a treatment assignment needs to be unmasked for safety reasons, the site PI will notify the SACCC, who will consult with the DAIT medical monitor. The DAIT medical monitor will review the circumstances and grant approval as indicated. In the event of a true medical emergency necessitating immediate unmasking during off-hours, the site pharmacist will confer with the study PI or designee prior to release of the treatment assignment to emergency treating personnel.

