8.3.2 Efficacy Analysis

8.3.2.1 Primary Efficacy Analysis

The primary efficacy analysis for this study is designed to test the scientific hypothesis that rituximab has a beneficial clinical impact on SSc-PAH as measured by improvement or stabilization in 6MWD between baseline to 24 weeks in patients treated with standard of care plus rituximab than in patients treated with standard of care plus placebo. Operationally for this study, this scientific hypothesis will be examined by formally testing the following statistical hypothesis:

H_0 : The mean change in 6MWD between baseline and 24 weeks does not differ between individuals treated with rituximab and those treated with placebo ($\delta_{\text{rituximab}} = \delta_{\text{placebo}}$ where $\delta_x = \text{mean 6MWD at 24 weeks} - \text{mean 6MWD at baseline}$)

versus

H_A : The mean change in 6MWD between baseline and 24 weeks is more beneficial in those individuals treated with rituximab than in those treated with placebo
($\delta_{\text{rituximab}} < \delta_{\text{placebo}}$ where $\delta_x = \text{mean 6MWD at 24 weeks} - \text{mean 6MWD at baseline}$)

While this hypothesis is inherently one-sided, two-sided tests will be used in the analysis. This primary hypothesis will be tested using a repeated measures random effects model to model change from baseline in 6MWD as the primary outcome and treatment as the primary predictor, controlling for visit day, limitations by musculoskeletal disease, baseline measures of 6MWD, and a treatment by visit day interaction. A random slope and intercept will be fit for each subject. An unstructured covariance matrix will be assumed for the random effects. More details on this analysis and sensitivity analyses will be defined in the Statistical Analysis Plan (SAP). The primary efficacy analysis will be based on the ITT population.

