11. CHANGES TO THE ANALYSES PLANNED IN THE PROTOCOL

[figure not shown]
1. Section 7.2.2: Primary endpoint:
 - a. Actual values rather than change from baseline in 6MWD will be used in the model.
 - b. Remove baseline measures of 6MWD as covariate
 - c. Use visit week rather than visit day
 - d. Addition of quadratic term for visit week
 - e. Remove limitations from musculoskeletal disease as a covariate. The number of “yes” occurrences is too sparse to inform the analysis.
2. Section 7.3.3: Clinical worsening: Protocol says “worsening of 6MWD by > 20% and a decrease in functional class” vs. corrected “worsening of 6MWD by > 20% and an increase in functional class”
3. Section 7.3.4: Analyses changed from using a logistic regression model to analyzing time to first change or addition of PAH medications.

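### The primary 6MWD model is valid, but it leaves out baseline PVR and time since diagnosis, two factors balanced at randomisation; prespecifying them with week interactions is a cheap, modest gain

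*SAP*

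**What the plan says.** Protocol 3.1.1 sets out the allocation method: "adaptive randomization procedure to maintain balance between treatment groups overall, by study site, with respect to disease severity as measured by PVR at baseline". It then names one more balancing factor: "with respect to time since diagnosis of SSc-PAH".

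Protocol 8.3.2.1 modelled change in 6MWD, "controlling for visit day, limitations by musculoskeletal disease, baseline measures of 6MWD, and a treatment by visit day interaction". SAP 7.2.2 replaces this with a "repeated measures random effect model to model the distance walked as a function of treatment, visit week and a treatment by visit week interaction", adds a quadratic week term, and fits random intercepts and slopes with a separate unstructured matrix for each arm. SAP section 11 declares the changes: "Actual values rather than change from baseline in 6MWD will be used in the model" and "Remove baseline measures of 6MWD as covariate". The baseline walk therefore becomes part of the response, and each arm keeps its own week-0 mean.

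SAP 7.1.1 gives a reason for omitting site (few subjects, many sites). I found no reason for omitting PVR or time since diagnosis. These two factors have the following routes into the 6MWD analyses:

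- The synopsis in both documents: "Additional covariates will be considered for this model as part of secondary analysis".
- Protocol 8.3.2.2: larger secondary models for covariates found to differ between arms. Disease duration and severity are named as candidates.
- Protocol 8.5.1 and SAP 7.2.3 item 5: covariates that differ between arms may be considered.
- Protocol 8.5.4 and SAP 7.4: optional subgroup analyses.

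**The concern.** A factor used to balance allocation is normally carried into the primary model. If it predicts outcome and is left out, the between-arm variance is overstated: the test becomes slightly conservative and some power is lost.

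The fallback routes do not repair this. Several of them open only when the arms differ on the covariate, and the randomisation system exists to prevent such differences on these two. All of them are secondary or optional, so they cannot change the primary test.

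The protocol sets enrolment at the largest attainable number (8.1) and describes the trial as underpowered (8.5.5). Data collected before treatment are the cheapest remaining source of precision.

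**Working it through.** **1. The plan's own figure.** Inputs from Protocol 8.1: difference 33 m, SD of change 58 m, 30 per arm, 20% dropout. From SAP 7.2.2: two-sided 0.05.

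- Evaluable per arm: 30 × 0.8 = 24.
- SE = 58 × √(2/24) = 16.74 m; 33/16.74 = 1.971.
- Normal power = Φ(1.971 − 1.960) = 0.504. With a noncentral t on 46 df it is 0.488.

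The stated 50% reproduces.

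**2. Why main effects alone do nothing.** The tested quantity is a difference in change. In the free-baseline model, a covariate that only shifts a subject's level cancels out of it. A check with an unbalanced binary factor gave a contrast variance of 265.45 with and without the main effect. The factors must be entered with a week interaction.

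**3. Gain from the two factors, by formula.** If they explain a share R² of the variance in change, SE becomes 16.74 × √(1 − R²). R² is assumed; the documents give no value.

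- R² = 5%: SE 16.32, ratio 2.022, power 0.525.
- R² = 10%: SE 15.88, ratio 2.078, power 0.547.

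**4. The same by simulation.** 60 subjects were allocated by minimisation, with 48 evaluable and residual SD 25 m. The analysis was of subject slopes, with and without the two factors, in 40,000 trials per setting. The minimisation settings are assumptions: Pocock-Simon, 20 sites, biased coin 0.8, binary factors.

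| R² | Power without | Power with | Change (points) | Size without | Size with |
|---|---|---|---|---|---|
| 0% | 0.502 | 0.496 | −0.6 | 0.050 | 0.050 |
| 5% | 0.507 | 0.524 | +1.7 | 0.047 | 0.050 |
| 10% | 0.508 | 0.547 | +3.9 | 0.041 | 0.049 |
| 20% | 0.505 | 0.597 | +9.2 | 0.036 | 0.050 |

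The 20% row is generous. The true between-subject variance of change is 58² − 2 × 25² = 3364 − 1250 = 2114, and 20% of 3364 is 673, so the factors would have to explain 673/2114 = 32% of it.

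**5. Common baseline mean (secondary).** Dropping the stand-alone treatment term uses the fact that randomised arms share an expected baseline. Generalised least squares was run for the SAP mean structure at weeks 0, 4, 12 and 24, with 24 per arm and change SD 58 m. The assumed grid has 27 settings: between-subject baseline SD 80 to 120 m, residual SD 15 to 35 m, intercept-slope correlation −0.3 to +0.3.

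- Contrast variance is multiplied by 0.88 to 0.92 at correlation −0.3, 0.96 to 1.00 at 0, and 0.93 to 1.00 at +0.3.
- Linear effect: 0 to +5.3 points of power, median 1.3; 15 of 27 settings gain less than 2 points.
- Late effect (nothing through week 12, then 33 m): −0.5 to about +5 points.
- Full effect by week 4: −3.7 to +11.9 points.

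These figures treat the covariances as known. With estimated covariances the ranges are −1.0 to +4.2 (linear) and −1.5 to +3.7 (late).

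**6. Why the effect path matters.** Treatment by week is linear, so the free-baseline contrast is 24 times the least-squares slope of the effect path. Week deviations from the mean of 10 are −10, −6, 2 and 14, with sum of squares 336.

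- Late path: 24 × (14 × 33)/336 = 33.0 m.
- Full effect by week 4: 24 × (−6 + 2 + 14) × 33/336 = 23.6 m.

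Forcing the arms together at week 0 changes these to 31.7–34.0 m and 21.0–27.0 m, depending on the covariances.

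**The case against.** The strongest reply is that nothing is broken. Putting baseline in the response vector and testing a difference in change is standard, the changes are declared in SAP section 11, and the planned power is met. A constrained baseline is a preference. That stands, and it is why this is offered as an improvement.

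On the two factors, the reply is that their value is unknown. The documents treat the relation between PVR and 6MWD as exploratory (Protocol 2.3, 3.2.4 and 8.3.4). They do not state the randomisation coding, and PVR may come from three cardiac-output methods (SAP 7.3.1). Protocol 8.3.2.2 also shows that disease duration and severity were considered as covariates. This stands as a limit on the size of the gain. It does not supply a prespecified route into the primary model, because that section depends on observed differences between arms.

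On the common baseline mean, the reply is largely right. The gain is near zero in many settings, gains above 3 points for a linear effect need a correlation of −0.3 that nothing in the documents supports, and the estimate depends on effect path. Protocol 1.5 makes an early full effect less likely but does not exclude it.

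A reader might infer something stronger: that removing baseline 6MWD as a covariate biases or invalidates the primary test, or that adjustment would rescue the trial's power. The documents support neither. Baseline is still used, as a response. And 80% power at 33 m needs an SE of about 33/2.80 = 11.8 m, a variance ratio of (11.8/16.74)² ≈ 0.50. Neither change alone comes near that.

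**Conclusion.** The point holds as a low-cost recommendation with medium confidence. The primary model is valid and delivers the power the protocol claims. Two named balancing factors are missing from it, without a stated reason and without a dependable route back in.

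Prespecifying them is worth about 2 to 4 points of power at 33 m if they explain 5 to 10% of the variance in change, and restores size from 0.041–0.047 to about 0.05. It costs about 0.6 point if they explain nothing. These figures rest on an assumed R² and on assumed minimisation settings.

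The common baseline mean is a smaller and less certain gain, and can lose power on some effect paths. No combined gain is claimed: the model with both changes and a separate covariance matrix per arm was not simulated.

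**What to change.** Before unblinding, amend SAP 7.2.2:

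1. **Main change.** Add baseline PVR and time since SSc-PAH diagnosis to the primary model, in the form the randomisation system used, each with its interaction with week. State that form in the SAP, since neither document gives it. Leave site out, as SAP 7.1.1 explains.
2. **Optional, smaller change.** Fit a common baseline mean by dropping the stand-alone treatment term and keeping treatment by week. Code the Screening walk as week 0, because it may precede Day 0 by up to 14 days (Protocol 6.5.1) and the constraint applies at week 0. Report the observed baseline arm difference descriptively: SAP 7.2.2 says model estimates "will be presented at baseline and Week 24, along with the differences between arms", and this model sets the baseline difference to zero. Because the estimate depends on effect path, a prespecified sensitivity analysis is a reasonable home for it.

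The cost is SAP wording only, with no new data and no new covariance parameters. With two-level factors, the first change adds four fixed-effect terms; the second removes one.

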8.3.2.2 Secondary Efficacy Analysis

All secondary analyses will be conducted in an exploratory fashion with p-values and confidence intervals presented as descriptive statistics with no adjustments for multiple comparisons. Tests will be two-sided and interval estimates will be generated at the 95% confidence level. As part of secondary analyses, appropriate contrasts will be constructed using model-based approaches. Larger models will be constructed for these comparisons with consideration of additional covariates that are found to differ between the treatment groups. Covariates may include, but are not limited to: study center, method of cardiac output, gender, disease duration and severity, and concomitant therapy use. All analyses will be repeated using the Per Protocol Population.

Change from baseline in PVR at Week 24 and percent change from baseline in PVR at Week 24 will be analyzed using an analysis of covariance, adjusting for treatment, method of cardiac output, and baseline PVR.

For the outcome time to clinical worsening, the two groups will be compared using survival approaches. Graphical summaries of time to clinical worsening will be generated using Kaplan-Meier survival curves with a log-rank test used to test for differences in the two arms. The two arms will also be compared after control of appropriate covariates using a Cox proportional hazards model.

For the proportion of subjects who changed or added PAH therapeutic agents, the treatment two arms will be compared using a logistic regression model, controlling for appropriate covariates. This will be done at the following time points: prior to week 24 and after week 24.

Longitudinal changes in continuous outcome measures including the subscales of the SF-36, the SHAQ, and DLCO will be compared across the two arms using linear mixed models. Initially the models will be used to describe changes between baseline and 24 weeks and

baseline and 48 weeks including only treatment, baseline levels of the outcome of interest, and an indicator if the measurement was affected by changed or new PAH therapeutic agents, with added models developed to assess the effect of other covariates.

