7.2.3. Sensitivity Analyses of the Primary Endpoint

The following sensitivity analyses will be performed:

1. Primary analyses performed on both PP populations.
2. If a subject's 6MWD decreased from Screening by more than 20% and a repeat 6MWD was performed, then models will be developed using both 6MWD values and also using just the second, confirmatory, value in the model.
3. Changes in background PAH medications prior to Week 24 (yes/no) will be added as a covariate to the model.
4. Missing data will not be imputed for the primary endpoint. However, sensitivity analyses may be performed to assess the robustness of the conclusions under different

assumptions. For example, missing data due to death of a subject prior to Week 24 would be handled differently than missing data due to a missed visit. A joint longitudinal/survival model to evaluate trends in clinical assessments under different assumptions about the underlying missing data mechanism may be considered, if appropriate.

5. Demographic and baseline characteristics that differ meaningfully between the two treatment groups (with or without a p-value <0.05) may be included in a covariate-adjusted model, as appropriate.
6. Time-varying covariates, like oxygen use during SMWD, may be added as appropriate.

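### The primary 6MWD contrast is 24 times a linear slope difference, so it equals the Week-24 difference in change only for some time courses, and no pre-specified analysis relaxes that constraint

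*SAP*

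**What the plan says.** SAP 7.2.2 will "model the distance walked as a function of treatment, visit week and a treatment by visit week interaction". It continues: "Additionally, a quadratic term for visit week will be included in the model". No treatment-by-week-squared term is named there or in the list of changes in SAP 11. Each subject has a random intercept and slope, with a separate unstructured covariance matrix per arm. The test is described as follows: "An appropriate contrast will be used to test the difference (baseline to Week 24) between treatment arms". Data run to Week 24, and "All unscheduled visits that occur prior to Week 24 will also be included in the analysis". For display, "Spaghetti plots and summary statistics including 25th percentile, mean, median, and 75th percentile will be plotted for each visit by treatment group", and model predictions are plotted beside the observed values.

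SAP 7.2.3 lists these sensitivity analyses: the per-protocol populations, alternative handling of repeat walks, a covariate for PAH-medication change, optional missing-data models, time-varying covariates, and adjustment (item 5) for "Demographic and baseline characteristics that differ meaningfully between the two treatment groups".

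The adaptive randomisation in protocol 3.1.1 is meant to "maintain balance between treatment groups overall, by study site, with respect to disease severity as measured by PVR at baseline", and also on time since diagnosis. Neither PVR nor time since diagnosis is in the primary model. Protocol 8.3.2.2 provides for larger secondary models with "consideration of additional covariates that are found to differ between the treatment groups".

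**The concern.** The hypothesis in SAP 7.2.2 is about mean change at 24 weeks. The model lets the arms diverge only along a straight line, because the curvature it adds is common to both arms and cancels from the between-arm comparison. The Week-24 contrast is then an extrapolated slope that takes in the Week-4 and Week-12 differences. If benefit does not grow linearly, the estimate can be too low or too high, depending on onset. The trial is planned at only 50% power. A reader might see misfit in the plots but would have no pre-specified Week-24 estimate or test to set beside the primary result.

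A smaller, separate matter is that leaving out the factors balanced at randomisation makes the standard errors too large and gives up precision, to the extent that those factors predict walk distance.

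**Working it through.** **Inputs from the documents.** 33 m versus 0 m, SD of change 58 m, 20% drop-out, stated power 50% (protocol 8.1); 30 per arm (synopsis); two-sided 5% (SAP 7.2.2); walks at Screening and Weeks 4, 12 and 24 (SAP 7.2.1).

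**Stated power.** With 24 per arm, SE = 58·√(2/24) = 16.7 m, 33/16.7 = 1.97, and power = Φ(1.97 − 1.96) ≈ 50%. The plan's figure is reproduced.

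**What the contrast estimates.** The week-squared term is common, and the random effects are an intercept and a slope. With complete data at Weeks 0, 4, 12 and 24, the generalised least-squares contrast therefore equals 24 times the ordinary slope of the arm differences. Mean week = 10; sum of squared deviations = 100 + 36 + 4 + 196 = 336. The weights 24·(t − 10)/336 are −0.714, −0.429, +0.143 and +1.000. With arms equal at baseline:

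contrast = d24 + 0.143·d12 − 0.429·d4.

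Mixed-model fits to 40 simulated data sets matched this identity to rounding error. The coefficients assume that the screening walk is coded as Week 0. It may be up to 14 days earlier, and SAP 7.2.2 does not say whether week is nominal or actual. Coded at Week −2, the weights become −0.73, −0.35, 0.16 and 0.92. Missing walks also shift them.

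**Size.** Assumed, because the documents do not give them: between-subject SD 80–110 m, residual SD 20–38 m, intercept–slope correlation −0.3 to 0.3, slope SD set so that the SD of change is 58 m, and 24 completers, 3 lost after Week 4 and 3 after Week 12 per arm. The true Week-24 effect is 33 m in every row.

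| d4/d12/d24 (m) | SAP estimate, complete data | SAP estimate, with drop-out | SAP power, with drop-out |
|---|---|---|---|
| 33/33/33 | 23.6 | 25–28 | 37–42% |
| 16.5/33/33 | 30.6 | 32–34 | 54–57% |
| 11/33/33 | 33.0 | 34–36 | 60–62% |
| 0/33/33 | 37.7 | 39–40 | 70–71% |
| 5.5/16.5/33 (linear) | 33.0 | 33.0 | 55–58% |
| 0/0/33 | 33.0 | 30–32 | 49–55% |

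First row: 33 + 0.143·33 − 0.429·33 = 23.6. The SAP model's SE with drop-out is 15.3–15.8 m. A spline in week with knots at 4 and 12 gives 33.0 m in every row, with power 53–59%. Its SE relative to the SAP model is −4% to +6% with complete data and −4% to +5% with drop-out.

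**The spline must replace the quadratic.** Suppose there is no treatment effect but both arms rise 20 m by Week 4. A treatment spline beside the common quadratic gives a spurious 3.3–4.6 m at Week 24 with drop-out. With the spline in both parts the result is 0.0 m.

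**Balancing factors.** If the two factors explain a share R² of the variance and are almost perfectly balanced, the unadjusted test has size 2·(1 − Φ(1.96/√(1 − R²))). At R² = 0, 5, 10 and 20% this is 5.0, 4.4, 3.9 and 2.8%. Adjusted power is 49, 51, 53 and 58%, against about 49% unadjusted (noncentral t, 24 per arm).

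**The case against.** A slope model is a reasonable economy with 60 subjects. The protocol already had a linear treatment-by-visit-day interaction (8.3.2.1), so the SAP did not introduce the constraint. Protocol 1.5 says that the effect may not be immediate, which makes the worst case, full benefit by Week 4, the least likely. Linear growth and a purely late effect carry no error with complete data. All of this stands, and it limits the size of the problem. It does not make the contrast a Week-24 difference.

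The plan also offers some protection. The plots in SAP 7.2.2 could show misfit, and SAP 7.3.2 lets plots of the same outcome shape the time trend. The plots are descriptive, however, and the SAP 7.3.2 provision is data-driven and belongs to the Week-48 model. Neither promises a Week-24 estimate or test.

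A reader might infer that the primary test should be replaced by a categorical-visit model. The documents do not support that. Early-endpoint walks would have to be filed under a later visit, which is carry-forward, although SAP 7.2.1 rules out imputation. Some unscheduled walks would be dropped, although SAP 7.1.2 and 7.2.2 keep them all. Nor is power always better: for 0/33/33 the SAP model has 70–71% against 53–59%, because it overstates the effect.

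A reader might also infer that covariates can enter only when the arms differ. Protocol 8.3.2.2 and SAP 7.3.2 allow optional additional covariate models without that condition. What remains is that the primary model omits the balanced factors, and that item 5 of SAP 7.2.3 admits baseline covariates only where the arms differ.

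**Conclusion.** The point holds as a gap in the pre-specified sensitivity analyses, not as an invalid primary test. On the SAP's wording, the contrast is 24 times a slope difference. For a true 33 m it gives 25–28 m with full benefit by Week 4, 39–40 m with onset between Weeks 4 and 12, and a value within about 3 m for the other courses examined. These figures rest on assumed time courses, variance components and drop-out timing; the documents give none of them.

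Two stronger readings fail. The estimate is not biased in a known direction, since the sign depends on onset. Type I error is not inflated when treatment has no effect at any visit. Only a benefit present early and gone by Week 24 would disturb the Week-24 null: 33/16.5/0 gives −0.429·33 + 0.143·16.5 = −11.8 m. The documents do not predict such a course.

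The omission of the balancing factors concerns efficiency and correct standard errors, not bias. Its size depends on an R² that the documents do not give, and it is nil if R² is zero.

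**What to change.** 1. Keep the SAP model as the primary test. Add to SAP 7.2.3 a pre-specified Week-24 contrast free of the linear constraint: a linear spline in actual week, with knots at Weeks 4 and 12, in both the common time course and the treatment interaction. It replaces the quadratic, has no treatment main effect, and keeps the SAP's random intercept and slope by arm. Every walk is then used at its own time, as SAP 7.1.2 and 7.2.2 require. The spline does assume straight lines between scheduled visits. State in SAP 7.2.2 whether week is nominal or actual, and how the screening walk is coded. A categorical-visit model may be added if its visit-assignment rule is written down and any carry-forward is acknowledged.

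2. Add baseline PVR and time since diagnosis to the primary model with their time interactions, and state how they are coded, since protocol 3.1.1 does not say. Centre can stay out, as SAP 7.1.1 has it.

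The cost is SAP wording and a few degrees of freedom. All the data are already collected, and the spline's SE is about −4% to +6% against the SAP model.
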